### 5.3.3 Exclusion Criteria

#### 5.3.3.1 Exclusion Criteria

- 1) Subject was enrolled in another clinical trial during this data collection period that might impact the outcomes of the present registry

## Clinical Investigation Plan

### 5.4 Subject Enrollment

Subjects are considered enrolled when research personnel at each participating center verify in the health record that all of the inclusion criteria and none of the exclusion criteria are met and, if applicable, local required privacy notice or consent rules have been followed.

### 5.5 Subject Withdrawal and Discontinuation

This is a retrospective data collection registry, so there will be no case of subject withdrawal and discontinuation.

### 5.6 Number of Subjects

Data on a minimum of 220 attempted subjects will be included in order to have 190 evaluable subjects in the registry.

### 5.7 Total Expected Duration of the Clinical Investigation

The total expected duration of data collection is [REDACTED] from activation of the first site.

## 6.0 TREATMENT AND EVALUATION OF ENDPOINTS

As a data collection registry, research personnel at each participating center will collect all of the following data from medical records.

### 6.1 Assessment time points

#### 6.1.1 Baseline

The baseline refers to the measurements made within 3 months prior to an attempted implant of the Tendril™ STS 2088 lead in the LBBA.

- Demographics (if provided): sex at birth, age range
- Cardiovascular (CV) history and other significant medical conditions
- Cardiac medications
- Indications for pacemaker or CRT-P/D implant
- Intrinsic QRS duration and QRS morphology (if available)
- NYHA classification (if available)
- LVEF, LVEDV, and LVESV (if available)
- Primary indications for device implant

#### 6.1.2 Implant Procedure

The implant procedure is an attempt implant of the Tendril™ STS 2088 lead in the LBBA. Sites report the following measurements from patient's medical record.

## Clinical Investigation Plan

- Procedure and device-related adverse events
- Implant success or failure for an LBBAP lead and if not successful, reasons for unsuccessful implant
- Implanted device information
- Number of LBBAP lead repositioning attempts at implant procedure and reason(s) for repositioning
- Overall procedure time: skin-to-skin
- Implant procedure time: vascular access to lead fixation
- Fluoroscopy time and radiation dose
- Implant tools used (i.e., catheter, stylet, etc.): manufacturer, model #
- LBBAP capture threshold, pulse width, sense amplitude, and pacing impedance
- 12-lead ECGs (if available)
- Post-implantation fluoroscopic images in any views (if available)

LBBAP implantation is considered successful if at least one of the following is met,

- Anatomical confirmation of LBBAP with fluoroscopic images (i.e., spatially oriented LBBAP lead implant using RAO or LAO view and contrast injection in RV chamber to confirm deep septal implantation for LBBAP)
- Unipolar-paced QRS morphology demonstrated a Qr or qR pattern in lead V1
- Identification of LBB potential on the sensed electrogram
- Demonstration of transition from nonselective to selective LBB/LV septal capture during threshold testing
- Stimulation to R-wave peak time in lead V5 or V6 < 90 ms

### 6.1.3 Follow-ups

The post-attempt follow-up visit for LBBAP occurs at 6 months ( $\pm 3$  months), and 12 months (-2, 4 months, optional), considering standard clinical practice.

- LBBAP capture threshold, pulse width, sense amplitude, and pacing impedance
- Adverse event (as applicable)
- Device programming (if available)
- Revision or explant (as applicable)
- Paced QRS duration (if available)
- NYHA classification (if available)
- LVEF, LVEDV, and LVESV (if available)

## Clinical Investigation Plan

### 6.2 Schedule of Events

CIP Activity	Baseline (≤ 3 months prior to an attempted implant of LBBAP, required)	Implant Attempt (required)	6 Month (±3 months post-attempt, required)*	12 Month (-2, +4 months post- attempt, optional)*
Data transfer notification/Informed consent process (if required by EC/IRB)	X			
Demographics (if provided)	X			
CV history and other significant medical conditions	X			
Implant indication	X			
Cardiac Medications	X			
QRS duration and QRS morphology** (if available)	X	X	X	X
NYHA classification (if available)	X		X	X
LVEF, LVEDV, LVESV (if available)	X	X	X	X
12-lead ECGs (if available)		X		
Post-implantation fluoroscopic images in any views (if available)		X		
Implanted device Information		X		
Number of LBBAP lead repositioning attempts and reason(s) for repositioning		X		
Procedure/fluoroscopy times/radiation dose		X		
Implant tools information		X		
LBBAP capture threshold, pulse width, sense amplitude, lead impedance		X	X	X
Adverse Event		(X)	(X)	(X)
Death	(X)	(X)	(X)	(X)
Product Out of Service		(X)	(X)	(X)
System Revision		(X)	(X)	(X)

(x) if applicable

\* If there are multiple visits within the visit window, the closest visit to 6 and 12 months will be captured using the scheduled follow-up CRF and other visit(s) will be captured using the unscheduled follow-up CRF.

\*\* Intrinsic QRS morphology is only applicable at baseline

### 7.0 Adverse Events

To comply with worldwide standards and guidelines on clinical investigation adverse event reporting, the Sponsor has adopted uniform and worldwide applicable standard definitions and reporting timelines to be used and adhered to by the investigators.

## Clinical Investigation Plan

### 7.1 Definition

#### 7.1.1 Adverse Event

An Adverse Event (AE) is any untoward medical occurrence, unintended disease or injury, or untoward clinical signs (including abnormal laboratory findings) in subjects, users or other persons, in the context of a clinical investigation, whether or not related to the investigational medical device.

As part of ISO14155 Section 3.2, the Adverse Event definition has the following notes:

**Note 1:** This definition includes events related to the investigational medical device or the comparator.

**Note 2:** This definition includes events related to the procedures involved.

**Note 3:** For users or other persons, this definition is restricted to events related to the use of investigational medical devices or comparators.

#### 7.1.2 Serious Adverse Event

Serious Adverse Event (SAE) is an AE that led to any of the following:

- a) death,
- b) serious deterioration in the health of the subject, that resulted in any of the following:
  - 1. life-threatening illness or injury,
  - 2. permanent impairment of a body structure or a body function,
  - 3. hospitalization or prolongation of patient hospitalization,
  - 4. medical or surgical intervention to prevent life threatening illness or injury or permanent impairment to a body structure or a body function.
  - 5. chronic disease
- c) fetal distress, fetal death or a congenital physical or mental impairment or birth defect.

**Note:** A planned hospitalization for a pre-existing condition, or a procedure required by the CIP without a serious deterioration in health, is not considered a SAE.

### 7.2 Device Relationship

Determination of whether there is a reasonable possibility that an investigational product or device under investigation caused or contributed to an AE is to be **determined by the Investigator** and recorded on the appropriate CRF form. Determination should be based on the assessment of temporal relationships, evidence of alternative etiology, medical/biologic plausibility and patient condition (pre-existing condition).

### 7.3 Adverse Event Reporting

#### 7.3.1 Adverse Event Reporting

General Adverse Event Reporting

## Clinical Investigation Plan

Sites will collect information on **all procedure and device-related adverse events, whether serious or not, and all death events** and report to the Sponsor on an Adverse Event CRF. Sites should update the Adverse Event CRF with additional information regarding the event as the information becomes available.

Unchanged, chronic, non-worsening or pre-existing conditions are not AEs and should not be reported.

### Serious Adverse Event Reporting

The investigator must report all **procedure and device-related SAEs** to the Sponsor as soon as possible.

Sites must record the date the site staff became aware that the event met the criteria of a reportable event as per this protocol in the source document. The Investigator will further report the applicable events to the local IRB/EC according to the institution's IRB/EC reporting requirements (if applicable).

### **7.3.2 Adverse Event Reporting to Country Regulatory Authorities by the Sponsor**

The Sponsor will report the procedure or device-related SAEs to the country regulatory authority per local requirements.

## **8.0 STATISTICAL CONSIDERATIONS**

The following section describes the statistical methods for the clinical investigation. Additional details on statistical analyses, including justification of clinical investigation design, sensitivity analyses, poolability analyses, subgroup analyses and analysis of descriptive endpoints, will be maintained in a separate Statistical Analysis Plan (SAP).

### **8.1 Analysis Populations**

#### **8.1.1 Enrolled Population**

This analysis population will include enrolled subjects who have been attempted to implant for the Tendril™ STS 2088 lead in the LBBA.

#### **8.1.2 Successfully Implanted Population**

The successfully implanted population includes enrolled subjects who are successfully implanted with the Tendril STS 2088 lead in the left bundle branch area (refer to Section 6.1.2).

### **8.2 Statistical Analyses**

#### **8.2.1 Primary Safety Endpoint Analysis**

The primary safety endpoint evaluates freedom from LBBAP lead-related SAEs through 6 months post-implant attempt.

The hypothesis is formally expressed as:

## Clinical Investigation Plan

$H_0$ : Freedom from LBBAP lead related SADEs  $\leq 81.2\%$   
 $H_1$ : Freedom from LBBAP lead related SADEs  $> 81.2\%$

The primary safety endpoint will be estimated as a binomial proportion and the 97.5% lower confidence bound (LCB) will be calculated using the Clopper-Pearson exact method. The null hypothesis is rejected at the 2.5% significance level if the LCB is greater than the performance goal (PG) of 81.2%. The p-value from a one-sided exact test for the binomial proportion will also be calculated and compared to the 0.025 significance level.

This analysis will be performed on the enrolled population, and the primary safety analysis will use evaluable subjects (refer to Section 8.3.1).

### 8.2.2 Primary Effectiveness Endpoint Analysis

The primary effectiveness endpoint evaluates the composite success rate of acceptable capture thresholds and sense amplitudes for LBBAP at 6 months post-implant.

The hypothesis is formally expressed as:

$H_0$ : Composite success rate  $\leq 80\%$   
 $H_1$ : Composite success rate  $> 80\%$

Parameter	Acceptable values
Pacing voltage	Pacing threshold $\leq 2.0\text{V}$
Sense amplitude	LBBA sense amplitude $\geq 5.0\text{ mV}$ or $\geq$ value at implant

**Success Criteria:** A subject will be considered to have met the primary effectiveness endpoint if: the pacing threshold voltage  $\leq 2.0\text{ V}$  and LBBA sense amplitude is  $\geq 5.0\text{ mV}$  or  $\geq$  value at implant at 6 months. For subjects that do not have LBBA amplitude measured due to active tachyarrhythmias or any other heart rhythm conditions or procedures which prevent sense amplitude from being measured, success will be determined from the pacing threshold only. For subjects that do not have pacing threshold measured, due to active tachyarrhythmias or any other heart rhythm conditions or procedures which prevent pacing threshold from being measured, success will be determined from LBBA sense amplitude only. Subjects that do not have LBBA sense amplitude and pacing voltage, both of which are unobtainable due to active tachyarrhythmias or any other heart rhythm conditions or procedures which prevent pacing threshold from being measured, will be excluded from the analysis.

The success rate will be estimated as a binomial proportion and the 97.5% LCB of the rate will be calculated using the Clopper-Pearson exact method. The null hypothesis is rejected as the 2.5% significance level if the LCB exceeds the PG of 80%. The p-value from a one-sided exact test for the binomial proportion will also be calculated and compared to the 0.025 significance level.

## Clinical Investigation Plan

This analysis will be performed on the successfully implanted population, and the primary effectiveness analysis will use last observation carried forward (LOCF) method. Sensitivity analysis will be performed using multiple imputation.

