### 8.6 Procedures for Accounting for Missing Data

The primary safety endpoint analysis will include evaluable subjects only. The primary effectiveness endpoint analysis will use LOCF method to impute missing 6-month data and sensitivity analyses will be performed using multiple imputation. All other outcome measures will be based on the available data, with no imputation for missing values.

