## Statistical Analysis Plan

Parameter	Acceptable values
Pacing voltage	Pacing threshold $\leq$ 2.0V
Sense amplitude	LBBA sense amplitude $\geq$ 5.0 mV or $\geq$ value at implant

**Success Criteria:** A subject will be considered to have met the primary effectiveness endpoint if the pacing threshold voltage  $\leq$  2.0 V and LBBA sense amplitude is  $\geq$  5.0 mV or  $\geq$  value at implant through 6 months. For subjects that do not have LBBA amplitude measured due to active tachyarrhythmias or any other heart rhythm conditions or procedures which prevent sensing amplitude from being measured, success will be determined from the pacing threshold only. For subjects that do not have pacing threshold measured, due to active tachyarrhythmias or any other heart rhythm conditions or procedures which prevent pacing threshold from being measured, success will be determined from LBBA amplitude only. Subjects that do not have LBBA amplitude and pacing voltage, both of which are unobtainable due to active tachyarrhythmias or any other heart rhythm conditions or procedures which prevent pacing threshold from being measured, will be excluded from the analysis.

The success rate will be estimated as a binomial proportion and the 97.5% LCB of the rate will be calculated using the Clopper-Pearson exact method. The null hypothesis will be rejected at the 2.5% significance level if the LCB exceeds the PG of 80%. The p-value from a one-sided exact test for the binomial proportion will also be calculated and compared to the 0.025 significance level.

This analysis will be performed on the successfully implanted population, and the primary effectiveness analysis will use the last observation carried forward (LOCF) method.

The primary effectiveness endpoint performance goal derivations are provided in Appendix A.

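### In the readable text, LOCF for the 6-month effectiveness endpoint does not bar the implant reading, and a carried implant amplitude meets the implant-value limb by being compared with itself

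*Protocol*

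**What the plan says.** **Missing data.** Protocol 8.2.2 states that "the primary effectiveness analysis will use last observation carried forward (LOCF) method". Protocol 8.6 gives the purpose: "The primary effectiveness endpoint analysis will use LOCF method to impute missing 6-month data". SAP 2.3.2 repeats that "the primary effectiveness analysis will use the last observation carried forward (LOCF) method". None of these sentences says which visit may be carried or sets an earliest time. SAP 2.9, on missing data, is redacted at the point where it would name the effectiveness method. Multiple imputation is planned as a sensitivity analysis (protocol 8.2.2, SAP 2.3.2.1); its model in SAP Appendix B is redacted.

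**Success rule.** Protocol 8.2.2 requires a pacing threshold of 2.0 V or less together with an amplitude that is at least 5.0 mV or at least the "value at implant at 6 months". Readings missing for rhythm or procedure reasons have their own rule: one component decides alone, or the subject is excluded when there is neither reading, "both of which are unobtainable due to active tachyarrhythmias or any other heart rhythm conditions or procedures" being the condition. LOCF is left with the other missing readings.

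**Readings available.** The row "LBBAP capture threshold, pulse width, sense amplitude, lead impedance" in protocol 6.2 is marked at implant, 6 months (± 3) and optional 12 months (−2, +4). Where several visits fall in a window, the closest one is the scheduled visit and "other visit(s) will be captured using the unscheduled follow-up CRF".

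**Who enters the analysis.** Protocol 6.1.2 says that "LBBAP implantation is considered successful if at least one of the following is met" and then lists imaging, ECG and electrogram criteria. None is a limit on threshold or sensed amplitude.

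**The concern.** The endpoint is meant to show that the lead paces and senses acceptably at 6 months. The implant-value limb is there for a lead that starts with a low amplitude and keeps it. It needs two readings taken at different times. If the implant reading stands in for the 6-month reading, there is only one, and the limb is met whatever its value.

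For such a subject sensing cannot fail, and the composite rests on the threshold. If the threshold is carried from implant as well, the subject can count as a 6-month success with no electrical evidence after implant. The self-comparison changes the outcome only for a carried subject whose implant amplitude was below 5.0 mV, whose threshold was 2.0 V or less, and who would in truth have failed at 6 months. Each such change is towards success, on a co-primary endpoint that must be met for study success (SAP 2.7).

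**Working it through.** **1. Which reading LOCF can reach.** Scheduled readings are at implant, 3 to 9 months, and optionally 10 to 16 months. A forward carry cannot use the 12-month visit. With no reading in the 6-month window, the last earlier reading is an unscheduled one if it exists, otherwise implant.

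**2. The identity.** Let A0 be the implant amplitude and A6 the value used at 6 months. Sensing passes if A6 ≥ 5.0 mV or A6 ≥ A0. With A6 = A0 the second condition is always true, for example at A0 = 3 mV. Protocol 6.1.2 sets no amplitude limit, so such a value can enter the successfully implanted population. The composite is not automatic: the threshold must still be ≤ 2.0 V.

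**3. The plan's own test.** Inputs: 190 evaluable subjects, 85% power and one-sided 2.5% (protocol 8.3.2); goal 80%, exact binomial test with Clopper-Pearson bound (protocol 8.2.2).
- Smallest r with P(X ≥ r | 190, 0.80) ≤ 0.025: r = 163 (163/190 = 85.8%), exact size 0.02497.
- Lower bound: 0.80002 at 163 and 0.7941 at 162. At that margin one subject decides the result.
- The planned success rate is redacted. Solving P(X ≥ 163 | 190, p) = 0.85 gives p = 0.8797, about 88%. At 0.88, power is 0.853 and 190 is the smallest n reaching 85%. The stated 190 is consistent with a rate of about 88%, but this is not an independent reproduction.

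**4. Effect of the self-comparison (illustration).** Neither share below is in the documents. Let m be the share of subjects carried from implant and w the share of those wrongly passed. With true success 80%, the apparent rate is 0.80 + m·w, the false-success rate is P(X ≥ 163 | 190, 0.80 + m·w), and the mean number wrongly passed is 190·m·w.

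| m | w = 0.05 | w = 0.10 | w = 0.20 |
|---|---|---|---|
| 0.01 | 2.6% | 2.7% | 2.9% |
| 0.02 | 2.7% | 2.9% | 3.4% |
| 0.05 | 3.0% | 3.6% | 5.2% |

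The mean number wrongly passed runs from 190 × 0.01 × 0.05 = 0.1 to 190 × 0.05 × 0.20 = 1.9. If carried subjects also have 80% true success, only 20% of them are true failures, so w = 0.20 means that every one is rescued. It is a ceiling. If the carried success rate equals the true rate of the missing subjects, there is no inflation.

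**5. Dropping these subjects instead.** Let t be the true success rate of those dropped, with 80% overall. The rest then have rate (0.80 − m·t)/(1 − m).

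| Dropped | n | Cut-off | t = 0.80 | t = 0.70 | t = 0.60 |
|---|---|---|---|---|---|
| 4 (m = 0.02) | 186 | 160 | 2.2% | 2.5% | 2.9% |
| 10 (m = 0.05) | 180 | 155 | 2.2% | 3.2% | 4.7% |

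The 2.2% values come from the steps of the exact test, not from less bias.

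**6. Power after dropping, at p = 0.8797 to 0.88.** 85% at n = 190, 83% at 186, 81 to 82% at 180. Because the test moves in steps, power across 180 to 189 ranges from 78% (n = 184) to 84% (n = 185).

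**The case against.** **The rule may already exist.** SAP 2.9 is redacted just where a carry rule would stand. SAP 5.0 defines LOCB (last observation carried backward), which no readable text uses, so undisclosed carry detail is likely. Protocol 8.0 leaves further analysis detail to the SAP. A reader might infer that the plan nowhere names the source visit; the documents do not support that, since redacted text is not absent text. What stands is that the readable protocol sentences do not bar the implant reading.

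**SAP 2.4.2 points both ways.** It expects some subjects without evaluable threshold or amplitude. That shows missing readings are anticipated, but it also fits a plan that does not carry implant values. It settles nothing.

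**The group is small.** Eligibility requires records through 6 months (± 3). The 6-month visit is required, and its electrical row lacks the if-available qualifier given to QRS, NYHA class and LVEF. The window is six months wide, and unscheduled readings are collected. This stands, although the eligibility criteria do not themselves demand an electrical reading.

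**The size rests on assumed shares, and one error is left out.** A carried implant threshold above 2.0 V would fail a subject who might pass at 6 months. Both stand. The self-comparison errs only towards success, but LOCF as a whole need not.

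**Dropping the subjects is not clearly better.** With 10 dropped at 70% true success the false-success rate is 3.2%, above the 3.0% at the low end for carrying 5%. This stands and shapes the fix.

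**Multiple imputation is planned.** It tests dependence on LOCF, but as a sensitivity analysis it does not change the primary decision.

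**Conclusion.** The concern holds for the readable text, as a minor point. The rule as written would let an implant amplitude below 5.0 mV pass the 6-month sensing criterion by comparison with itself.

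Two stronger readings should be resisted. One is that a carried subject passes the whole endpoint automatically: the 2.0 V threshold limit still applies. The other is that the type I error is shown to be inflated. The 2.6 to 5.2% range depends on assumed shares (1 to 5% carried, 5 to 20% of those wrongly passed), its upper end is a ceiling, and it amounts to 0.1 to 1.9 subjects on average. The documents give no count of subjects who would be carried from implant.

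The conclusion also assumes that the redacted part of SAP 2.9 does not already exclude the implant reading. If it does, only the protocol wording needs attention.

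**What to change.** In protocol 8.2.2 and 8.6 and SAP 2.3.2 and 2.9, state one of the following:

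- **Preferred:** only post-implant readings may be carried into the 6-month assessment.
- **Minimum:** the implant-value limb does not apply to a carried implant amplitude, which must then reach 5.0 mV.

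If implant readings are not carried, report how many subjects have no post-implant reading, and present the primary result beside the planned multiple-imputation analysis. Leaving these subjects out makes the primary analysis complete-case for them, which can itself bias it (step 5 of the working). If SAP 2.9 already restricts the source, align the protocol with it.

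**Cost.** Wording in four sections and no new data. The minimum option gives slightly fewer successes and keeps the subjects in. The preferred option gives slightly fewer evaluable subjects: if 4 or 10 of 190 drop out, power falls from about 85% to about 83% or 81 to 82%, with the step effect noted above and the back-solved success rate of about 88%.

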#### 8.3.2 Primary Effectiveness Endpoint

[REDACTED] The minimum sample size to reject the null hypothesis is 190 evaluable subjects with 85% power at 2.5% one-sided significance level.

[REDACTED]

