### 2.4.2 Primary Effectiveness Endpoint

The assumed success rate is based on the LBBAP data in the literature. Given the lack of individual patient-level data for electrical performance, the overall implant success rate is used as a proxy to evaluate the composite success rate of acceptable capture thresholds and sense amplitudes for LBBAP through 6 months post-implant. According to the meta-analysis of 10 LBBAP studies, the overall range of LBBAP implant success rate with consideration of LBBAP electrical performance was [REDACTED] with [REDACTED] of success rate from meta-analysis.

Assuming:

- A composite success rate of [REDACTED]
- [REDACTED] power
- Binomial exact test
- One-sided alpha of 0.025
- Performance goal of 80%

The minimum sample size to reject the null hypothesis is [REDACTED] evaluable patients. Assuming approximately [REDACTED] of subjects will not have a successful LBBAP implant per protocol, and that about [REDACTED] of subjects will not have evaluable capture threshold and/or sense amplitudes, [REDACTED] subjects will be enrolled to ensure that [REDACTED] subjects are evaluable for the primary effectiveness endpoint. Evaluable subjects are defined in Section 2.3.2.

The sample size calculation was performed using the PASS 15 Tests for One Proportion module.

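### As visibly written, LOCF can score an LBBA lead explanted, replaced or taken out of service before 6 months as an effectiveness success

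*Protocol*

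**What the plan says.** The effectiveness analysis covers subjects whose implant met the procedural definition in CIP 6.1.2. Neither CIP 8.1.2 nor SAP 2.1.2 requires the lead to be in service at 6 months.

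A subject succeeds if the pacing threshold is at most 2.0 V and the sense amplitude is at least 5.0 mV or at least the subject's own implant value. CIP 8.2.2 assesses this at 6 months; SAP 2.3.2 says through 6 months.

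For missing values, CIP 8.2.2 states that "the primary effectiveness analysis will use last observation carried forward (LOCF) method", and CIP 8.6 that the analysis "will use LOCF method to impute missing 6-month data". SAP 2.3.2 also names LOCF. Multiple imputation is the stated sensitivity analysis.

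Both documents have a separate clause for measurements prevented by tachyarrhythmia, other rhythm conditions or procedures. If one measure is missing, the other decides; if both are unobtainable, the subject is excluded.

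Lead failure is recorded: CIP 6.1.3 lists "Revision or explant (as applicable"), and the schedule in CIP 6.2 has System Revision and Product Out of Service items. The visible success criteria do not use these items.

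**The concern.** A lead removed before the 6-month visit has no 6-month reading, so LOCF supplies an earlier one. If that is the implant reading, it equals the implant value and passes sensing by definition. Only the threshold limit remains, and it is judged on a reading taken while the lead was still working.

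Eligibility makes this a realistic case. CIP 5.3.2 requires records through 6 months (± 3 months), which should screen out much ordinary loss to follow-up. It does not require a functioning LBBA lead, so a patient whose lead was explanted but who stayed under care still qualifies.

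Loss of capture, poor sensing and dislodgement are what an electrical-performance endpoint should detect. Counting them as successes, or dropping them, biases the rate upward against the 80% goal.

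**Working it through.** **Inputs.**
- CIP 8.3.2: "The minimum sample size to reject the null hypothesis is 190 evaluable subjects with 85% power at 2.5% one-sided significance level".
- CIP 8.2.2: "the 97.5% LCB of the rate will be calculated using the Clopper-Pearson exact method", and the null is rejected "if the LCB exceeds the PG of 80" percent.
- CIP 5.6: "Data on a minimum of 220 attempted subjects will be included in order to have 190 evaluable subjects in the registry". The implied loss is 1 − 190/220 = 13.6%.
- SAP 2.4.2 gives the assumed rate as "A composite success rate of [REDACTED"], so it has to be back-solved.
- The share of subjects whose lead failed and who lack a 6-month reading, k, is not given. I assume 1% to 3%, or 1.9 to 5.7 subjects of 190.

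**Formulas.** P(X ≥ r) = Σ from x = r to n of C(n,x) pˣ(1−p)ⁿ⁻ˣ. The lower bound (LCB) for x successes is the 0.025 quantile of Beta(x, n−x+1).

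**1. The plan's own figure.** For n = 190 and p = 0.80, the smallest r with P(X ≥ r) ≤ 0.025 is 163 (85.8%), with exact size 0.02497. At a true rate of 88% the power is 85.3%, and 190 is the smallest n that reaches 85% at that rate. The stated 190 is therefore consistent with an assumed rate of about 88%. It cannot be strictly reproduced while that rate is redacted.

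**2. Sensitivity at the pass mark.**

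| Successes of 190 | LCB | One-sided p | Goal met |
|---|---|---|---|
| 163 | 80.002% | 0.025 | yes |
| 162 | 79.41% | 0.039 | no |
| 160 | 78.2% | 0.084 | no |

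At the pass mark, one lead scored differently decides the result.

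**3. Type I error if failed leads become successes (LOCF).** Let the true rate with these leads counted as failures be 80%. If all of the share k convert, the analysed rate is 0.80 + k and the error is P(X ≥ 163) at that rate.

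**4. Type I error if they are excluded (procedures clause).** The denominator falls to about 190(1−k) and the analysed rate becomes 0.80/(1−k), which is 0.808, 0.816 and 0.825. The pass mark is recomputed for each n.

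| k | LOCF: analysed rate | LOCF: error | Exclusion: n, pass mark | Exclusion: exact size at 80% | Exclusion: error |
|---|---|---|---|---|---|
| 0 | 0.80 | 2.5% | 190, 163 | 2.5% | 2.5% |
| 1% | 0.81 | 5.2% | 188, 162 | 1.8% | 3.4% |
| 2% | 0.82 | 10.0% | 186, 160 | 2.2% | 7.0% |
| 3% | 0.83 | 17.8% | 184, 159 | 1.6% | 9.2% |

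**5. Partial conversion.** If 2% of subjects have such a lead but half of them have a failing last reading, only 1% convert and the LOCF error is 5.2%, not 10.0%.

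**6. Power under the fix.** If 88% was the rate before reclassification, the rate becomes 0.88 − k. Power goes from 85.3% to 73.3% (k = 1%), 58.4% (2%) and 42.9% (3%).

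**The case against.** **Redaction.** The missing-data sentence in SAP 2.9 is blacked out, as is all of Appendix B, and CIP 8.3 is partly redacted. The SAP abbreviation list defines last observation carried backward, which the visible text never uses, so the hidden text may hold finer rules. This stands. A reader might infer that the plan has no rule for these leads; the documents support only that the visible scoring text has none.

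**Multiple imputation.** A reader might also infer that the sensitivity analysis has the same flaw. The imputation model is redacted, so this cannot be said.

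**Failing last readings.** LOCF carries the last recorded value, and visits between the scheduled ones are collected. A lead revised for a high threshold may have an out-of-range reading on file, which LOCF would carry as a failure. Under the SAP's through-6-months wording, an earlier failing value might also count. Both points stand and shrink the effect. Neither helps when every earlier reading was acceptable.

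**Repositioned leads.** It is tempting to say that LOCF rewards repositioning. A repositioned lead with its own 6-month value has nothing missing, so LOCF is not used. The gap there is only that the visible text does not say how a revised lead is scored.

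**The exclusion clause.** An explant could be read as a procedure that prevents measurement, which leads to exclusion. That inflates less (step 4), but it still does not count the lead as a failure, and it competes with LOCF for the same subject.

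**The safety endpoint.** A revision that is a lead-related SADE counts in the safety endpoint, and SAP 2.7 requires both endpoints to be met. Such failures are not invisible to the study, but the effectiveness rate stays uncorrected.

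**Conclusion.** The point holds as a gap in the visible scoring rules. They allow a lead that failed before 6 months to be a success under LOCF or to be excluded, and under neither reading does the loss of the lead itself make the subject a failure. At n = 190 the one-sided error would rise from 2.5% to at most 5.2%, 10.0% or 17.8% if 1%, 2% or 3% of subjects had such a lead, or to about 3.4%, 7.0% or 9.2% under exclusion.

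These figures assume a true rate of exactly 80% and that every such lead converts or is excluded. The shares are assumptions, and the figures should not be read as the registry's actual error rate. The sample size of 190 is not in dispute. The conclusion would change if the redacted SAP text already scores these leads as failures. Clarification is warranted because the endpoint is primary and supports an indication expansion.

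**What to change.** Add to CIP 8.2.2 and SAP 2.3.2, before the endpoint is analysed: a successfully implanted subject whose LBBA lead was revised, replaced, explanted or taken out of service for capture, sensing or dislodgement reasons before the 6-month measurement is scored as an effectiveness failure. State that LOCF and the exclusion clause apply only to leads still in service, and say how a lead removed for an unrelated reason is handled. Align CIP 8.6, and align SAP 2.9 and Appendix B if their redacted text differs.

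No new data items are needed, since the System Revision and Product Out of Service items are already collected. The cost is in the result: the success rate falls by the share of such leads, and power falls as in step 6, to about 73% at 1% if 88% was the planning rate. Because the derivation of the 80% goal in SAP Appendix A is redacted, the sponsor should also confirm that the goal was set on a definition that treats these leads the same way.
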